5. Nielsen, T., et al., Maternal and infant characteristics associated with maternal opioid overdose in the year following delivery. *Addiction*, 2019.

2. * Describe the study hypothesis and/or research questions. Use lay language whenever possible.

1. How feasible and acceptable is the technology-based intervention with content on NOWS, child welfare interactions, and the postpartum transition compared to a brochure for pregnant patients receiving MOUD?

We hypothesize that integration of the technology based intervention into a busy prenatal clinic will be as feasible as the brochure and more acceptable to patients.

2. How effective is the intervention for improving exploratory outcomes (i.e., mental health, recovery, functioning, and quality of life)?

3. * Describe the study's specific aims or goals. Use lay language whenever possible.

The primary objectives of this RCT are to assess the feasibility and acceptability of the technology-based educational intervention with content on NOWS, child welfare interactions, and the postpartum transition compared to a brochure for pregnant patients receiving MOUD.

Additional exploratory objectives are to evaluate intervention effectiveness on improving outcomes (i.e., mental health, recovery, functioning, and quality of life).

4. * Describe the scientific benefit or importance of the knowledge to be gained:

Integrated treatment programs for pregnant and parenting women with OUD, like ours at VCU, need better educational tools specific to the postpartum transition. The proposed study will provide critical feasibility and acceptability data to improve the novel patient education materials and inform future studies evaluating clinically applicable patient centered interventions focused on the mother-infant dyad affected by OUD. Ultimately, implementation of clinically applicable patient-centered interventions focused on the mother-infant dyad could have broad positive impacts on the long-term health of families in the opioid crisis.

5. * Describe any potential for direct benefits to participants in this study:

Participants may gain additional knowledge to help them prepare for the pregnancy to postpartum transition and take care of their recovery.

6. * Describe any potential for direct social impact in this study . For example, any engagement with specific communities to respond to community-identified needs, or ways the study will strengthen the well-being of the specific communities if applicable:

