View Follow up visit scripts	Project BETTER Follow-up Visits Script.docx	0.01	10/11/2021 [name]	7:36 PM Study reminders/communications	Yes
View [name] CV	CEM_CV_08.15.21_BT.pdf	0.01	10/10/2021 [name]	9:23 PM CV/Biosketch	Yes
View [name] CV	[name] CV .pdf	0.01	10/10/2021 [name]	5:44 PM CV/Biosketch	Not Applicable

Study Population

1. * Provide the maximum number of individuals that

1. May participate in any study interaction or intervention (Including screening, consenting, and study activities)

AND/OR

2. You obtain any data/specimens about (regardless of identifiability)

at VCU and at other sites under the VCU IRB's oversight. See the help text for additional guidance.

70

2. If this is a multi-Center Project, what is the maximum anticipated number of subjects across all sites?

N/A

3. * Provide justification for the sample size by explaining how you arrived at the expected number of participants and why this number is adequate for answering the research questions:

Target sample size: N=30 (15 per study condition)

As this is a pilot feasibility trial, 30 study participants is the recommended sample size (Browne, 1995).

Browne R.H. (1995) On the use of a pilot sample for sample size determination. Statistics in Medicine 14, 1933–1940.

Based on our prior experience, we anticipate about 20% of eligible participants we approach will not be interested in the study, which will be about 10.

Additionally, we will abstract information from the medical record on the birth hospitalization for participants' infants, which includes an additional 30.

This makes a total of 70 as above.

4. * List the study inclusion criteria:

- 1) Female
- 2) ≥18 years of age
- 3) Meet criteria for Opioid Use Disorder
- 4) Currently receiving MOUD pharmacotherapy (including buprenorphine, buprenorphine/naloxone, or methadone)
- 5) Pregnant (<34 weeks EGA)
- 6) Engaged in treatment at OB MOTIVATE for ≤10 weeks during the current pregnancy OR engaged in community-based OUD treatment for ≤10 weeks during the current pregnancy

5. * List the study exclusion criteria:

- 1) Considering/planning adoption
- 2) Present with a serious cognitive/psychiatric impairment
- 3) Existing language barriers making true informed consent impossible

6. Justify the inclusion and exclusion criteria if you are either targeting, or excluding, a particular segment of the population / community. Provide a description of the group/organization/community and provide a rationale.

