
Pregnant people in treatment for OUD will be selected because the patient education intervention targets this specific population. We want to make sure the program is feasible and acceptable to this unique population.

Background, Rationale & Goals Section Complete

Protocol Progress:

- **INITIAL SETUP**
- **BACKGROUND, RATIONALE & GOALS**
- ③ RESEARCH PLAN
- ④ CONSENT PLAN
- ⑤ RISKS, PRIVACY & CONFIDENTIALITY
- ⑥ POPULATIONS WITH SPECIAL CONSIDERATIONS
- ⑦ INSTITUTIONAL REQUIREMENTS
- ⑧ DOCUMENTS

Click Continue below to go to the next section

Study Procedures

1. * Describe the study hypothesis and/or research questions. Use lay language whenever possible.

1. How feasible and acceptable is the technology-based intervention with content on NOWS, child welfare interactions, and the postpartum transition compared to a brochure for pregnant patients receiving MOUD?

We hypothesize that integration of the technology based intervention into a busy prenatal clinic will be as feasible as the brochure and more acceptable to patients.

2. How effective is the intervention for improving exploratory outcomes (i.e., mental health, recovery, functioning, and quality of life)?

2. * Describe the study's specific aims or goals. Use lay language whenever possible.

The primary objectives of this RCT are to assess the feasibility and acceptability of the technology-based educational intervention with content on NOWS, child welfare interactions, and the postpartum transition compared to a brochure for pregnant patients receiving MOUD.

Additional exploratory objectives are to evaluate intervention effectiveness on improving outcomes (i.e., mental health, recovery, functioning, and quality of life).

3. * Choose all types of recruitment materials that may be used and upload them below:

- E-mail invitations
- Phone Solicitation scripts (i.e. cold calls or random-digit-dialing)
- Flyers, Mailed Letters or Newspaper/TV/Radio Ads
- TelegRAM announcements
- Website text
- Study-specific web sites (provide the design and text)
- Social Media
- EPIC MyChart Patient Portal research study descriptions
- Psychology Research Participant Pool (SONA) study descriptions
- Scripts for announcements made to groups
- Other recruitment document
- No recruitment materials

4. * If Other was selected above, describe the recruitment document that will be used:

In person recruitment script

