3. Potential participants will be called and/or emailed by the research assistant (up to 4 times over 10 weeks) or approached in the clinic when they arrive for a scheduled clinic appointments while waiting to see their provider in the private exam rooms. If the potential participant does not answer the phone, the research assistant will leave a generic voicemail without any identifying information (i.e., "This is (RA name) calling from VCU health about potential participation in a research study. If you are interested in learning more, please return the call to XXX-XXX-XXXX"). When the RA talks to the potential participants, they will confirm their eligibility for the study verbally using the eligibility form (see uploaded recruitment scripts).

**Potential participants who use the recruitment flyer QR code to provide contact information will be called and/or emailed by the research assistant (up to 4 times over 10 weeks). If the potential participant does not answer the phone, the research assistant will leave a generic voicemail without any identifying information (i.e., "This is (RA name) calling from VCU health about potential participation in a research study. If you are interested in learning more, please return the call to XXX-XXX-XXXX"). When the RA talks to the potential participants, they will confirm their eligibility for the study verbally using the eligibility form (see uploaded recruitment scripts).

6. * Does this study have a separate protocol document (i.e. a multisite or sponsor's protocol) that contains a detailed description of the study's methodology?

Yes
 No

7. * Upload the separate protocol document, and in the response below, provide all of the following information:

1. Identify which specific sections of the protocol describe the study design and procedures.
2. A statement explaining the study design
3. A lay language overview of all research activities/procedures
4. For multisite studies, a description of whether there are any local changes to the protocol's procedures, and if so, what those changes are (i.e. different, omitted, or additional procedures)
5. Any necessary clarifications of the protocol's content (i.e. what local standard of care or routine practice is)

1. Entire Standard Operating Procedures (SOP) document

2. Pilot feasibility randomized controlled trial comparing technology-based modules (intervention) to a brochure (control)

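### Does the expectation that the modules are as feasible as the brochure need a margin or a precision target behind N=30?

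*Combined protocol and SAP*

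**What the plan says.** Study Population, question 3, asks how the number was reached and "why this number is adequate for answering the research questions". The answer gives a target of 30, or 15 per condition, and says "As this is a pilot feasibility trial, 30 study participants is the recommended sample size", with one methods citation. The rest of that answer builds a head-count of 70 for the ethics board.

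The hypothesis is stated in Background, Rationale and Goals, question 2, and repeated in Study Procedures, question 1: "integration of the technology based intervention into a busy prenatal clinic will be as feasible as the brochure and more acceptable to patients". The aims that follow in both sections are worded differently: "The primary objectives of this RCT are to assess the feasibility and acceptability of the technology-based educational intervention", compared with a brochure. Effects on mental health, recovery, functioning and quality of life are called exploratory.

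Study Procedures, question 7, labels the design a pilot feasibility randomized trial. For design and procedures it points to the "Entire Standard Operating Procedures (SOP) document". That document is listed as approved, but its text is not part of the file.

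**The concern.** The form asks for a link between the sample size and the research questions, and the answer offers only a convention for pilots. The hypothesis, meanwhile, is comparative. Taken literally, a claim that one arm is as feasible as the other is an equivalence or non-inferiority claim, which needs a margin and normally a sample several times larger. The second half, that the modules are more acceptable, is a superiority claim, and it has no effect size behind it.

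The risk is in the reporting. With 15 per arm, an unremarkable difference could be presented as confirming equal feasibility although the data would also fit a considerable deficit. Feasibility is a primary objective and the results are meant to inform later studies, so such a misreading would matter.

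**Working it through.** **What the plan's own figures allow.** No significance level, power, rate, margin or interval width is given, so no formula can reproduce 30. Only the counts can be checked: 15 + 15 = 30 participants, and 30 participants + 10 decliners + 30 infants = 70. The 10 decliners are loosely derived: a 20% refusal rate gives 30/0.8 = 37.5, so 38 approached and 8 declining, whereas 10 of 40 is 25%. This affects a ceiling for the ethics board and has no bearing on the analysis.

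**Assumptions for the rest (none is in the documents).** A yes/no feasibility measure per participant, 15 evaluable per arm, equal true rates, and margins of 20 or 30 points.

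**Precision within an arm.** The Wilson 95% interval is [p + z²/(2n) ± z√(p(1−p)/n + z²/(4n²))] / (1 + z²/n). For 12/15, with p = 0.8, n = 15 and z = 1.96, it is (0.928 ± 0.240)/1.256, or 55% to 93%.

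**Precision of the difference.** With equal counts, Newcombe's lower limit is −√[(p − l)² + (u − p)²], where l and u are the Wilson limits. For 12/15 in each arm this is −√(0.252² + 0.130²) = −0.283. Other cases, lower limit in points:

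| Observed in each arm | Newcombe 95% | Agresti-Caffo 95% | Newcombe 90% | Agresti-Caffo 90% |
|---|---|---|---|---|
| 12/15 | −28.3 | −28.5 | −23.9 | −23.9 |
| 14/15 | −23.8 | −21.7 | −19.1 | −18.2 |
| 15/15 | −20.4 | −15.8 | −15.3 | −13.3 |

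With 12 evaluable per arm (an assumed 20% loss), 10/12 in each arm gives about ±31 points.

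**Chance of excluding a deficit when the arms are truly equal.** Exact binomial, true rates 60% to 95%, range over the same two methods:

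| Margin | 95% interval | 90% interval |
|---|---|---|
| 20 points | 0.191 to 0.527 | 0.298 to 0.665 |
| 30 points | 0.431 to 0.902 | 0.575 to 0.969 |

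**A formal non-inferiority design, for scale.** With one-sided 2.5%, 80% power and p = 0.8 in both arms, n per arm = (1.960 + 0.842)² × 2 × 0.8 × 0.2 / 0.20² = 62.8, so 63 for a 20-point margin. With 15 per arm the standard error is √(2 × 0.16/15) = 0.146. Power is then Φ(0.20/0.146 − 1.96) = 28%, and the margin supportable with 80% power is 2.80 × 0.146 = 41 points.

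**Reading the arithmetic against the text.** These figures show that 15 per arm cannot carry a confirmatory claim. They would expose a fault only if the plan made one. It states no margin, alpha, test, success threshold or go/no-go rule. Both hypothesis fields ask for lay language, and the sentence reads naturally as what the team expects to see. The stated objectives are to assess, and the stated use is to improve the materials and inform later work. For those purposes, an interval of 55% to 93% around an observed 80% is informative.

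**The case for a change.** The best case for a change is that it would be cheap and would settle in advance what the pilot may conclude. Question 3 asks for a link to the research questions and does not get one. The hypothesis goes further than the objectives, and nothing in the file forbids reading a null difference as equality. A few sentences would close that door without touching the sample.

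The factual part stands: no margin, precision or named measure appears in the text available, and 15 per arm is imprecise for a comparison. The conclusion does not follow, for three reasons.

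- The harm is argued from silence. No section plans to treat a non-significant difference as equality, and the document that holds the design detail cannot be inspected, so it may already name a measure or a rule.
- The figures rest on an assumed endpoint. The hypothesis is about integrating the modules into a busy clinic, which may be a matter of workflow or delivery and not a per-participant rate. The chance of excluding a deficit runs from about 19% to 97% across the margins, levels and rates above, so no single figure describes the trial.
- A shared completion measure would not compare like with like. The modules take about 25 minutes each, or 3 × 25 = 75 minutes in all, and contain attention checks (Active Internet Data Collection, question 3). The brochure takes 25 to 45 minutes in total, and no such checks are described for it. A gap in completion could reflect length or ascertainment.

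**Conclusion.** The concern does not call for a change. The plan leaves unstated the precision that 30 participants will give. This is a gap in detail that any analyst of a two-arm pilot fills in the same way: rates or scores per arm and a difference, each with an interval, and no equivalence, non-inferiority or superiority conclusion on feasibility or acceptability. Under an assumed 80% binary rate with 15 evaluable per arm, that means roughly 55% to 93% per arm and ±28 points for the difference. Stating this in the form would be harmless, but it would change no estimate, sample size or procedure. The judgement rests on reading the hypothesis as a lay expectation, which the objectives and the design label support. It would differ if the operating procedures document announced a formal test of equal feasibility with these numbers. Whether the cited paper supports 30 was not assessed.

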3. Following consent, participants will complete the first study visit, a baseline assessment (electronic survey & brief RA questions). Then participants will be randomized (1:1) to either the technology-based modules (intervention) group or the brochure (control) group. Randomization and intervention introduction can be completed at the same time of the other first study visit procedures (ie, pre-survey) or as a supplemental unpaid visit based on participant preference (ie, if the participant wants to complete the pre-survey remotely and the intervention introduction in person). Participants will be provided access via email/text to the modules or the electronic brochure (based on randomization) for three weeks. Following the 3-week study intervention period, participants will complete two follow-up study visits (electronic survey & brief RA questions): 1) during pregnancy within two weeks of intervention timeframe (Study visit 2) and 2) within 4-8 weeks postpartum (Study visit 3). Enrolled, randomized participants not completing Study visit 2 within 5 weeks of study condition introduction, but wishing to do so, will be reviewed by the PI on a case-by-case basis for the opportunity of continued study participation. Specifically, if the participant is no longer pregnant, study continuation will not be allowed; if still pregnant, the PI will consider the option of study continuation (e.g., completion of follow-up visit 1) for the participant. For each study visit, we will also obtain health information (as per secondary data page and uploaded document) via the health record after participants have agreed to the HIPAA authorization in the consent form. Participants will be compensated \$20 per study visit (up to \$60 total).

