Brochure condition: Provision of written materials to patients is often a component of standard care. Therefore, participants in the brochure condition will be provided a paper copy and/or provided an electronic pdf of the study brochure via email/text (in order to facilitate ease of participation for those who prefer remote study completion) covering content on the pregnancy to postpartum transition, NOWS, and child welfare interactions. There is a QR code within the brochure that leads to a website with additional information on the three educational topic areas. The brochure is uploaded in the documents.

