This page asks for details about the social/behavioral intervention, task, or environmental manipulation in the research.

Interventions include both physical procedures by which information is gathered and manipulations of the subject or the subject's environment that are performed for research purposes. This might include activities such as playing computer games, performing a task, thought/cognition activities, environmental manipulations, and educational activities.

If the study only involves surveys, interviews, or secondary data collection, go back to the Project Details page and uncheck "Social/Behavioral interventions or experimentation / Tasks / Environmental manipulations" in Question 1.

1. * Describe the duration of the social/behavioral intervention, task, or environmental manipulation:

Module condition: Participants in the module condition will have access to the 3 modules in the technology-based intervention covering content on the pregnancy to postpartum transition, NOWS, and child welfare interactions (approximately 25-minutes each). Modules can be reviewed in the OB MOTIVATE clinic using research tablets or they can be reviewed remotely on a personal device in any order the participant chooses. Modules deliver information via the Computerized Intervention Authoring System, Version 3 (CIAS 3.0) using professionally produced videos and an interactive avatar using behavioral techniques, such as psychoeducation and aspects of motivational interviewing. Participants in the technology-based modules intervention condition will access the modules for 3 weeks through a link via email/text. Participants will enter their Study ID into the modules. No personal identifying information will be collected or housed in CIAS 3.0 modules. All participants in this condition will be oriented to the intervention with the RA via the program introduction (5 minutes).

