Brochure condition: Provision of written materials to patients is often a component of standard care. Therefore, participants in the brochure condition will be provided a paper copy and/or provided an electronic pdf of the study brochure via email/text (in order to facilitate ease of participation for those who prefer remote study completion) covering content on the pregnancy to postpartum transition, NOWS, and child welfare interactions. There is a QR code within the brochure that leads to a website with additional information on the three educational topic areas. The participants will have 3 weeks to review the brochure content (including the additional educational content through the QR code). Review of all brochure information will take approximately 25-45 minutes.

2. * Describe any potential harms or discomforts that participants could experience during the intervention activity:

Few risks are expected by taking part in this study. There is the possibility that participants may experience some fatigue and/or discomfort when reviewing the content in the brochure or modules. The content in the brochure and modules is a review of information covered in standard medical treatment for this population. Participants will be informed of their right to refuse or stop study participation at any time, and their right to refuse to answer any questions that make them uncomfortable. The following message will also be provided in each of the modules and on the brochure, "If you have concerns or are experiencing a negative reaction to any of the content, please contact the research assistant at [contact]."

Participants may be disappointed if they are not assigned to their preferred group or are not able to access the technology-based modules throughout the study. Following the conclusion of the study, research team plans to make the technology-based modules accessible to clinicians and patients.

3. * Will the intervention activity be physically invasive or painful?

- Yes
- No

4. * Describe the impact the intervention activity will have on participants, including the nature and duration of any impact(s):

The brochure content will take approximately 25-45 minutes to review. The three modules each take approximately 25 minutes to review. Review of content based on study condition will take some sustained attention that will end after the content has been reviewed.

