5. * In the investigator's opinion, is there any reason to think that the participants will find the intervention activity offensive or embarrassing? Explain why or why not.

No, the content in the brochure and modules is a review of information covered in standard medical treatment for this patient population. As part of standard prenatal care for people with opioid use disorder, medical providers review information about the pregnancy to postpartum transition, neonatal opioid withdrawal syndrome, and interactions with child welfare. The modules and brochure provide the same information using a different medium. Additionally, the brochure and modules were designed using a process of iterative modification grounded in formative data from both

patients and providers. Preliminary evaluation data indicate the modules and brochure are highly acceptable to patients and feasible to complete in a clinical setting and remotely. Based on our preliminary evaluation, no patients have found the modules or brochure to be offensive or embarrassing. In fact, some patients noted they are more comfortable receiving the information using the modules and brochure rather than being told directly from their medical provider.

Active Internet Data Collection

1. * Describe the platform/technology chosen for collecting the data and transmitting data securely over the internet. If proposing a non-VCU approved platform, give the rationale for selecting the technology instead of a VCU-approved platform.

RedCap, a VCU approved platform, will be used to store/collect all study visit data (surveys, RA questions, chart abstraction).

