The Computerized Intervention Authoring System, Version 3 (CIAS 3.0) is an authoring tool that allows creation or editing of electronic screening and intervention packages without the need of a programmer. Interventions built using CIAS feature a synthetic text to speech engine that reads all questions and speaks aloud to the participant; synchronous interactivity, natural language reflections, branching logic, a clean user interface, and the ability to easily incorporate specific images, graphs, figures, text, or videos. CIAS applications are HIPAA compliant with encryption of all data in transit and at rest, and are hosted on a HIPAA-compliant cloud server. CIAS 3.0 is cross-platform compatible, meaning that it deploys readily on any device including those running the Android or Apple mobile operating systems. CIAS versions 1.0 and 2.0 have been used with thousands of participants, and consistently received extremely high satisfaction ratings (e.g., Naar-King et al., 2013; Ondersma et al., 2005, 2007, 2012), including with high risk and low SES samples.

For the current study, no identifiable data will be collected using the CIAS 3.0 software. Unique hyperlinks to the CIAS 3.0 modules, associated with participant study ID's, will be provided via email/text by the study RA.

2. * Describe how data will be linked or unlinked to identifiers including email addresses, names, and/or IP address.

A Study ID will be assigned to each participant upon study enrollment. All study visit data (survey, RA questions, chart abstraction) will be stored in RedCap and will only be labelled with participant's Study ID already associated with the study. The key linking the participant information and Study ID will be kept in a separate secure VCU RedCap database.

The participants will enter their Study ID into the CIAS platform when they complete the modules. Participants will not enter any identifying information into the modules.

A unique VCU email address used by the research team only will be used to send emails with the links for the RedCap surveys, modules, and the brochure.

3. * How will you protect your data collection from fraudulent responses:

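### Does a three-week limit on the module links, set against a brochure that can be kept, undermine the exploratory comparison at Visit 3?

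*Combined protocol and SAP*

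**What the plan says.** Study Procedures, question 7, item 3 sets one nominal period for both arms: "Participants will be provided access via email/text to the modules or the electronic brochure (based on randomization) for three weeks". Two follow-up visits come after it. Visit 2 is during pregnancy, within two weeks of the intervention period, and Visit 3 is at 4-8 weeks postpartum. For a woman who has not completed Visit 2 within 5 weeks of introduction, "if the participant is no longer pregnant, study continuation will not be allowed".

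Delivery differs by arm. Under the brochure condition in the same answer, participants "will be provided a paper copy and/or provided an electronic pdf of the study brochure via email/text", with a QR code leading to further web content. In Behavioral Intervention/Task Details, question 1, module participants "will access the modules for 3 weeks through a link via email/text", whereas for the brochure arm "The participants will have 3 weeks to review the brochure content". Active Internet Data Collection, question 1 describes the module links as "Unique hyperlinks to the CIAS 3.0 modules, associated with participant study" IDs, so the study team could in principle close them. No section says that it does.

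The primary objectives are feasibility and acceptability (Background, Rationale and Goals, question 3). Effectiveness is secondary to these: "Additional exploratory objectives are to evaluate intervention effectiveness on improving outcomes".

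**The concern.** Three weeks is worded as access for the modules and as time to review for the brochure. Only the first can be enforced, because nobody collects a leaflet or deletes a PDF. If the module links are closed at week 3, the brochure arm can reread its material through late pregnancy, birth and the first weeks with the infant, which is the period the content is meant to prepare women for. The module arm cannot.

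The protocol also says that "The modules and brochure provide the same information using a different medium", which can be read as making medium the intended difference between the arms. On that reading, any arm difference at Visit 3 in mental health, recovery, functioning or quality of life would combine format with retained access. The text mentions no record of use after week 3, so the two could not be separated later. A false lead from this pilot could then carry into the larger studies it is meant to inform.

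**Working it through.** **1. Length of the gap.** The protocol gives no figure, so it has to be derived.

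Inputs from the protocol: access ends at introduction + 3 weeks; Visit 3 is at delivery + 4 to 8 weeks; entry is before 34 weeks of gestation. Assumed: delivery at 37-40 weeks. Illustrative: introduction at 20 weeks (no lower gestational limit is given).

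Gap = delivery week − (introduction week + 3) + 4 to 8.

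- Floor from the protocol alone: Visit 2 follows the 3 weeks and takes place in pregnancy, so delivery falls after access ends and the gap is at least 4 weeks.
- Introduction at 33w6d (33.86): access ends at 36.86. Delivery is 0.14 to 3.14 weeks later, so the gap is 0.14 + 4 = 4.1 to 3.14 + 8 = 11.1 weeks.
- Introduction at 20 weeks: access ends at 23. Delivery is 14 to 17 weeks later, so the gap is 18 to 25 weeks.

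These are calendar gaps in availability, not differences in use or in outcome.

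**2. Gap at Visit 2.** The ordinary limit is 5 weeks from introduction: 5 − 3 = at most 2 weeks after the review period, unless the investigator allows a late visit case by case.

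**3. What contrast is intended.** The sentence about the same information in a different medium answers Behavioral Intervention/Task Details, question 5, which asks whether participants might find the activity offensive or embarrassing. The sentence before it says that medical providers already cover these topics in standard prenatal care. The answer ends with patients who were more comfortable with the modules and brochure than with hearing the information from a provider. In context, both materials are being compared with counselling by a provider. The sentence does not define the contrast between arms.

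The design statement is in Study Procedures, question 7, item 2: a pilot feasibility trial of modules (intervention) against a brochure (control). The brochure is justified by the common use of written materials in standard care. That is a comparison of packages.

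**4. Is format otherwise isolated?**

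| Feature | Module arm | Brochure arm |
|---|---|---|
| Planned review time | 3 × 25 = 75 min | 25-45 min |
| Interactive avatar, aspects of motivational interviewing | yes | none described |
| Orientation with the research assistant | 5 min | none described |
| Can be kept after week 3 | not stated | paper or PDF, yes |

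The module arm has 75 − 45 = 30 to 75 − 25 = 50 more minutes of content. Equal retained access would leave the first three rows unchanged.

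**5. What the exploratory contrasts can show.** With n per arm, 80% power and two-sided 5% (both assumed, as the protocol states neither), the normal approximation gives a detectable difference of (1.96 + 0.84) × √(2/n) standard deviations:

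- n = 15: 2.80 × 0.365 = 1.02
- n = 12 (an illustrative 20% loss): 2.80 × 0.408 = 1.14

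**The case for a change.** The best case for a change is that it would be cheap and that the opportunity passes. One wording edit and one question at Visit 3 would cost almost nothing, and late use that is not recorded at the time can be recovered only by recall. Behavioral Intervention/Task Details, question 2 also anticipates disappointment among participants who cannot use the modules throughout the study, with wider access planned only after it ends. That fits links that close early, although it may describe the brochure arm instead. The protocol does not label its Visit 3 contrasts as package comparisons, so a reader could credit a difference, or its absence, to format.

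Part of this stands. The wording for the two arms is not the same, a brochure can be kept, and the trial cannot speak to format alone. But the last limit holds whatever is done about access. The Visit 3 survey and research assistant form are not in the public text and may already ask about later use. The operating procedures, which the protocol names as its full design description, may already say what happens to the links. Reopening links during the trial would create two versions of the module exposure among 30 women, which is harder to interpret than a single stated rule.

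**Conclusion.** No change is needed. Whether the links close is a gap that the study team can fill from its own procedures and report. Having a keepable leaflet as the control is a fair choice, because it is how written material works in ordinary care. Run as written, the trial gives a sound comparison of a module package with a brochure package, and an analyst would describe it that way without being told.

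The most that can be at stake is the interpretation of exploratory Visit 3 outcomes, over an availability gap of at least 4 weeks and perhaps 18 to 25 weeks for earlier entrants. Three conditions would all have to hold: the links close at week 3, exploratory outcomes are compared by arm at Visit 3 (the text does not assign outcomes to visits), and later use goes unrecorded. Even then, if rereading helps, retained brochures would more plausibly shrink a module advantage than create one. The size of any such effect is unknown. Feasibility and acceptability, the primary aims, are essentially untouched.

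This conclusion rests on reading the design statement as a package comparison. It would weaken if the operating procedures declared format alone to be the target.
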